3.3 Exclusion Criteria

A subject will be excluded from participation if any of the following apply:

- 1. Subject has a known or suspected hypersensitivity to ASP3772 its comparators or any components of the formulations used.
- 2. Subject has had previous exposure with ASP3772.
- 3. Subject has had known previous exposure with PPSV23.
- 4. Subject has received PCV13 or any other licensed or investigational pneumococcal vaccine at any time. (**Note**: This exclusion criterion is not applicable to Group 3; those subjects 65 to 85 years of age who previously received immunization with PCV13. Prior PCV13 immunization should have taken place no less than 10 months and no more than 2 years prior to study vaccine administration. These subjects are eligible to be enrolled in the nonrandomized arm of Stage 2, Group 3.
- 5. Subject has a history of microbiologically-proven invasive disease caused by S. pneumoniae.
- 6. Subject has an immune disorder(s) (including autoimmune disease) and/or clinical conditions requiring immunosuppressive drugs.
- 7. Subject has any evidence of any unstable or active clinically significant cardiovascular, gastrointestinal, endocrine, hematologic, hepatic, immunologic, metabolic, urologic, pulmonary, neurologic, dermatologic, psychiatric, renal and/or other major disease or malignancy, as judged by the investigator, e.g., uncontrolled hypertension, uncontrolled diabetes, heart failure, uncontrolled chronic obstructive pulmonary disease, end-stage renal disease.
- 8. Subject has history of illicit drug(s) or alcohol abuse that the investigator believes will interfere with the protocol requirements and/or a positive urine drug test (for Stage 1 subjects only) at screening.
- 9. Subject has any clinically significant history of allergic conditions including drug allergies, asthma or anaphylactic reactions, but excluding untreated asymptomatic seasonal allergies prior to study vaccine administration.
- 10. Subject has a coagulation disorder contraindicating intramuscular immunization.
- 11. Subject has a positive serology test for hepatitis B surface antigen (HBsAg), hepatitis A virus antibodies (immunoglobulin M), hepatitis C virus antibodies (anti-HCV) confirmed

02 Dec 2019 Astellas Page 47 of 111

- by reflex testing (HCV-RNA) or antibodies to human immunodeficiency virus (HIV) type 1 and/or type 2 at screening.
- 12. Subject has/had febrile illness (> 100.4°F oral equivalent) or symptomatic, viral, bacterial (including upper respiratory infection) or fungal (noncutaneous) infection within 1 week prior to day 1.
- 13. Subject has any clinically significant abnormality following the investigator's review of the physical examination, ECG and protocol defined clinical laboratory tests during screening.
- 14. Subject is unlikely to adhere to study procedures, keep appointments, is planning to relocate during the study or cannot be adequately followed for safety according to the protocol.
- 15. Subject has any other condition, which, in the opinion of the investigator, precludes the subject's participation in the study.
- 16. Subject has received any vaccines within 30 days prior of receipt of the study vaccine (exception: Influenza virus vaccine given according to recommended guidelines must be given at least 7 days prior to receiving study vaccine).
- 17. Subject has had significant blood loss, donated 1 unit (450 mL or more) or received transfusion of any blood or blood products within 60 days or donated plasma within 7 days prior to day 1.
- 18. Subject has received any systemically absorbed antibiotics during the 7-day period prior to day 1.

Waivers to the exclusion criteria will **NOT** be allowed.

4 IMMUNIZATION(S)

4.1 Identification of Investigational Products

4.1.1 Study Vaccine (ASP3772)

ASP3772 is a suspension containing 24 pneumococcal capsular PS serotypes. It consists of biotinylated PS complexed with a carrier protein. ASP3772 is supplied as a sterile suspension in single-dose vials and appears as grey/white suspension. It is administered as a single intramuscular injection via needle and syringe into the deltoid muscle of the right or left arm.

Each 0.5 mL dose of ASP3772 drug product is formulated to contain 1, 2 or 5 μg of each *S. pneumoniae* serotype 1, 2, 3, 4, 5, 6A, 6B, 7F, 8, 9N, 9V, 10A, 11A, 12F, 14, 15B, 17F, 18C, 19A, 19F, 20B, 22F, 23F and 33F PS as MAPS complexes. ASP3772 will be supplied by Astellas as single-use vials with respective dose. ASP3772 should be stored in refrigerator at 2°C to 8°C protected from exposure to light. Aseptic technique must be used for the preparation of ASP3772.

Detailed instructions for the storage, handling, preparation and administration of the ASP3772 injectable solution along with instructions for storage, handling and use of syringe and needle are provided in the pharmacy manual.

02 Dec 2019 Astellas Page 48 of 111

4.1.2 Comparative Vaccine(s)

4.1.2.1 Prevnar 13

Prevnar 13 (PCV13) is a suspension of pneumococcal capsular antigens of *S. pneumoniae* PS serotypes 1, 3, 4, 5, 6A, 6B, 7F, 9V, 14, 18C, 19A, 19F, 23F individually linked to a non-toxic diphtheria CRM197 protein. It is administered as a single intramuscular injection of 0.5 mL into the deltoid muscle of the right or left arm. PCV13 is supplied in a single-dose prefilled syringe by Astellas.

Detailed instructions for the storage, handling, preparation and administration of the Prevnar 13 prefilled syringe along with instructions for storage, handling and use of preferred syringe and needle are provided in the pharmacy manual or in the package insert.

4.1.2.2 Pneumovax 23

PPSV23 (pneumococcal vaccine polyvalent) is a capsular PS from *S. pneumoniae* serotypes 1, 2, 3, 4, 5, 6B, 7F, 8, 9N, 9V, 10A, 11A, 12F, 14, 15B, 17F, 18C, 19F, 19A, 20A, 22F, 23F, 33F in each 0.5 mL dose. It is administered as a single intramuscular injection of 0.5 mL solution into the deltoid muscle of the right or left arm. PPSV23 is supplied in a single-dose prefilled syringe by Astellas.

Detailed instructions for the storage, handling, preparation and administration of the PPSV23 prefilled syringe along with instructions for storage, handling and use of preferred syringe and needle are provided in the pharmacy manual or in the package insert.

4.2 Packaging and Labeling

All study vaccine(s) (ASP3772, PCV13 and PPSV23) used in this study will be prepared, packaged and labeled under the responsibility of qualified staff at Astellas Pharma Global Development Inc. (APGD) or sponsor's designee in accordance with APGD or sponsor's designee Standard Operating Procedures (SOPs), Good Manufacturing Practice (GMP) guidelines, ICH Good Clinical Practice (GCP) guidelines and applicable local laws/regulations.

Each vial will bear a label conforming to regulatory guidelines, GMP and local laws and regulations that identifies the contents as investigational vaccine. The study centers should store ASP3772, PCV13 and PPSV23 in original provided carton or packing, protected from sunlight and at a temperature indicated in pharmacy manual.

4.3 Study Vaccine Handling

Current ICH GCP Guidelines require the investigator to ensure that study vaccine deliveries from the sponsor are received by the investigator/or designee and that:

- Such deliveries are recorded,
- Study vaccine is handled and stored according to labeled storage conditions,
- Study vaccine with appropriate expiry/retest and is only dispensed to study subjects in accordance with the protocol, and
- Any unused study vaccine is returned to the sponsor.

02 Dec 2019 Astellas Page 49 of 111

Study vaccine inventory and accountability records will be kept by the study pharmacist. Study vaccine accountability throughout the study must be documented and reconciled. The following guidelines are therefore pertinent:

- The investigator, study pharmacist agrees not to supply study vaccines to any persons except the eligible subjects in this study in accordance with the protocol.
- The study pharmacist or designee will keep the study vaccines in a pharmacy or other locked and secure storage facility under controlled storage conditions, accessible only to those authorized by the investigator to dispense these study vaccines.
- A study vaccine inventory will be maintained by the study pharmacist or designee. The
 inventory will include details of material received and a clear record of when they were
 dispensed and to which subject.
- At the conclusion or termination of this study, study pharmacist or designee agrees to conduct a final vaccine supply inventory and to record the results of this inventory on the Vaccine Accountability Record or equivalent form in Interactive Response Technology (IRT) system. It must be possible to reconcile delivery records with those of used and/or returned study vaccine. Any discrepancies must be accounted for and documented. Appropriate forms of deliveries and returns must be signed by the site staff delegated this responsibility.
- The site staff must return study vaccine to the sponsor or designee at the end of the study or upon expiration unless otherwise approved by the sponsor.

4.4 Blinding

4.4.1 Blinding Method

This is an observer-blind study since the comparator has a unique syringe that the sponsor cannot duplicate. Subjects will be randomized at a 3:1 ratio (ASP3772:comparator vaccine PCV13) in a blinded fashion such that the investigator, clinical staff, nor the subject will know which agent is being administered. Only the pharmacist and designated staff, including the person(s) injecting the vaccine will be unblinded to study vaccine. The syringes will be masked prior to dosing to maintain the blind for subjects and all other personnel. The details regarding study blinding will be described in the pharmacy manual. The randomization number will be assigned based on information obtained from the IRT. The study will be unblinded to the investigator after the database lock.

The safety and tolerability data for dose escalation by the DEC will be reviewed under blinded conditions. If there are AEs that meet the criteria that could prohibit dose escalation, (i.e., a SAE, an AE of severe intensity, or 2 or more subjects experience a reactogenicity event of grade 3 or higher intensity), the study vaccine assignment for these subjects will be revealed to determine if these events are related to ASP3772. If 10% or more of the subjects within a cohort experience the same or related AE, the study vaccine assignment for those subjects will be revealed to determine if there is an imbalance in unsolicited AEs between ASP3772 and PCV13. The DEC can request the study vaccine assignment for 1 or more subjects.

4.4.2 Confirmation of the Indistinguishability of the Study Vaccines

Not applicable, as the comparator vaccines (PCV13 and PPSV23) are available in the form of pre-filled syringes and it is not possible to make the study vaccines indistinguishable. The investigational product and comparator will be sent to the site in an unblinded fashion for the unblinded staff at the site to handle.

4.4.3 Retention of the Assignment Schedule and Procedures for Study Vaccine Assignment Code Breaking

The randomization list and study medication blind will be maintained by the IRT system. The study pharmacist (or investigator's designee) will be unblinded to prepare vaccine for administration according to randomization code.

4.4.4 Breaking the Study Vaccine Assignment Code for Emergency

The study vaccine assignment code for each randomized subject will be provided by the IRT in the event of a medical emergency requiring knowledge of the study vaccine assigned to the subject. The IRT will be programmed with blind-breaking instructions that may only be requested by the investigator or subinvestigators designated to have access to perform blind-break. In case of a medical emergency, the investigator has the sole responsibility for determining if unblinding of subject's vaccine assignment is warranted. Subject safety must always be the first consideration in making such determination. If the investigator decides that unblinding is warranted, the investigator should make every effort to contact the sponsor prior to unblinding a subject's vaccine assignment unless this could delay emergency treatment for the subject.

The investigator must have confirmed functionality to access code-break through the IRT system and must have a designated back up (e.g., redundant processes) to support emergency unblinding requirements.

Prior to randomization, subjects should be provided with information that includes the site emergency contact number and back-up contact number in case of a medical emergency. Any unblinding by the investigational staff must be reported immediately to the sponsor and include an explanation of why the study vaccine was unblinded. If unblinding is associated with a SAE the investigator is to follow the instructions in [Section 5.5.5 Reporting of SAE].

Care should be taken to limit knowledge of the randomization arm, in case this could affect the blinding of other subjects or future trial assessment for the subject.

4.4.5 Breaking the Study Vaccine Assignment Code by the Sponsor

The sponsor and DEC may break the study vaccine assignment code for subjects who experience a Suspected Unexpected Serious Adverse Reaction (SUSAR), in order to determine if the individual case or a group of cases requires expedited regulatory reporting. Individual Emergency Codes will be provided to the limited staff who are responsible to break the codes for all SUSAR cases for reporting purposes.

02 Dec 2019 Astellas Page 51 of 111

4.5 Assignment and Allocation

At the Screening Visit, after the informed consent form (ICF) has been signed, site staff will access the IRT system, enter the subject's required information, and the subject will receive a subject number assignment through the IRT for use throughout the study.

Each cohort will be initiated with randomization of 1 sentinel subject each assigned to either ASP3772 or PCV13. Sentinel subjects need to be replaced if discontinued or unable to follow up for at least 7 days. The safety data from sentinel subjects will be reviewed by the DEC to make a decision to proceed with enrollment of the rest of the cohort. Subjects in the full cohort who meet the inclusion/exclusion criteria will be randomized in a 3:1 ratio (ASP3772:PCV13) according to the randomization schedules through IRT. In Stage 2, the randomization to study vaccine assignment will be stratified by age. Prior to study immunization, the site staff will access the IRT system in order to determine the randomly assigned study vaccine. The site personnel will dispense the study vaccine according to the IRT system's assignment. Specific procedures for randomization through the IRT are contained in the study procedures manual.

Subjects who subsequently meet the inclusion/exclusion criteria will be randomly assigned to receive either ASP3772 or PCV13. The randomization to study vaccine will be stratified by age.

The IRT vendor will generate the randomization schedule. To obtain the randomized study vaccine assignment for a subject, the pharmacist or designee will utilize an IRT system, which is available 7 days a week, 24 hours a day. After submitting required information about the eligible subject, the vaccine kit number assignment will be provided.

Study vaccine assignment will remain blinded to all site staff except the pharmacist, designated staff and the unblinded administrator.

If a subject is randomized but does not receive study vaccine, the kit number will not be used again. In this instance, the study vaccine assignment should only be known by the pharmacist and designated staff (i.e., the blind must be maintained as it is with all other subjects).

5 IMMUNIZATIONS AND EVALUATION

5.1 Dosing and Administration of Study Vaccine and Other Medications

5.1.1 Dose/Dose Regimen and Administration Period

Stage 1:

Adults 18 to 64 years of age - PCV13 Naïve Subjects (Group 1):

Subjects randomized to ASP3772 will receive a single immunization of ASP3772 as a 0.5 mL intramuscular injection on day 1 at 1 of 3 dose levels: 1, 2 or 5 µg of ASP3772 for Cohorts 1, 2 and 3, respectively. The subjects randomized to PCV13 will receive a single injection of the standard dose of PCV13 on day 1. Follow-up study visits will be conducted at 7 and 30 days postimmunization. The final study visit at day 180 may be conducted via telephone call.

02 Dec 2019 Astellas Page 52 of 111

Stage 2:

Elderly 65 to 85 years of age - PCV13 Naïve Subjects (Group 2):

Subjects randomized to ASP3772 will receive a single immunization of ASP3772 administered as a 0.5 mL intramuscular injection on day 1, at 1 of 3 dose levels: 1, 2 or 5 μg of ASP3772 for Cohorts 4, 5 and 6, respectively. The subjects randomized to PCV13 will receive a single 0.5 mL intramuscular injection of the standard dose of PCV13. Follow-up study visits will be conducted at 7 and 30 days postimmunization. The final study visit at day 180 may be conducted via telephone call.

Elderly 65 to 85 years of age - Previous PCV13 Exposed Subjects (Group 3):

A third group of nonrandomized subjects previously vaccinated with PCV13 will be enrolled and receive a booster immunization (single 0.5 mL intramuscular injection) with PPSV23 on day 1. A follow-up visit will be conducted at 30 days postimmunization and this visit will also serve as the final study visit.

5.1.2 Increase or Reduction in Dose of the Study Vaccine(s)

Decision Process for Dose Escalation:

After both sentinel subjects in a cohort have completed study procedures on day 7, the decision to open enrollment for the full cohort will be determined by DEC based on review of the Day 7 reactogenicity and safety data of those 2 sentinel subjects.

After all vaccinated subjects in a cohort have completed study procedures on day 7, the decision to dose escalate to next cohort within both stages will be determined by DEC based on the review of the following:

- Day 7 reactogenicity and safety data (AEs, ECG, clinical laboratory tests and vital signs) from the current cohort.
- Day 7 reactogenicity and safety data from all subjects of the preceding cohort(s).

To evaluate safety by DEC, day 7 data is needed from a minimum of 38 subjects in each cohort for Stage 1.

Stage 2 will commence based on DEC review of the following:

- Day 7 reactogenicity and safety data (AEs, ECG, clinical laboratory tests and vital signs) from all subjects in Stage 1.
- Day 30 safety data (AEs, ECG, clinical laboratory tests and vital signs) from all subjects in Stage 1.

To evaluate safety by DEC, day 7 data is needed from a minimum of 129 subjects in each cohort for Stage 2. Further details around the dose escalation process are located in the DEC charter.

02 Dec 2019 Astellas Page 53 of 111

Dose Escalation Criteria:

Depending on the nature, frequency and severity of the safety profile observed in the study, and the study vaccine received, the DEC will decide whether to:

- Proceed with dose escalation.
- Proceed from Stage 1 to Stage 2.
- Determine need of sentinel dosing in Stage 2 cohorts.
- Stop dose escalation.

Dose escalation may proceed unless 1 (or more) of the following apply in subject(s) receiving ASP3772:

- Two or more subjects experience an AE of severe intensity related to ASP3772 or 2 or more subject(s) experience a reactogenicity event of grade 3 or higher intensity.
- One or more subject(s) experience a SAE related to ASP3772.

Stopping criteria for study immunization are described in detail in [Section 5.1.5 Criteria for Continuation of Immunization].

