5.1.5 Criteria for Continuation of Immunization

Formal Stopping Rules for Individual Subjects:

Individual subjects will be discontinued from the study if:

- Subject is lost-to-follow-up despite reasonable efforts by the investigator to locate the subject.
- Subject voluntarily withdraws from the study at any time for any reason.

Formal Stopping Rules for Cohorts:

No additional subjects will be randomized or dosed in the study until the events below occurring in a subject who received ASP3772 are reviewed by the DEC and it is acceptable to resume cohort immunization.

- Unexplained death of a subject.
- Serious acute hypersensitivity reaction in a subject.
- One of the sentinel subjects experiences an AE of severe intensity related to ASP3772, when sentinel subjects are required.
- An SAE of the same character occurs in at least 2 subjects or 1 subject experiences a vaccine-related SAE.
- Grade 3 or higher lab abnormality considered related to the immunization occurs in 2 or more subjects [FDA Guidance for Industry, 2007].
- The same type of reactogenicity event assessed as Grade 3 or higher occurs in 2 or more subjects, or 1 of the sentinel subjects experiences a reactogenicity event assessed as Grade 3 or higher, using the FDA toxicity grading scale for preventative vaccines [FDA Guidance for Industry, 2007].
- An imbalance of unsolicited AEs between ASP3772 and PCV13 is observed.

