5.5 Adverse Events and Other Safety Aspects

5.5.1 Definition of Adverse Events

An AE is any untoward medical occurrence in a subject administered a study vaccine, and which does not necessarily have to have a causal relationship with this immunization. An AE can therefore be any unfavorable and unintended sign (including an abnormal laboratory finding), symptom, or disease (new or exacerbated) temporally associated with the use of a medicinal product whether or not considered related to the medicinal product.

In order to identify any events that may be associated with study procedures and could lead to a change in the conduct of the study, Astellas collects AEs even if the subject has not received study product. AE collection begins after the signing of the ICF and will be collected until 30 days after study vaccine administration or the subject is determined to be a screen failure.

Care will be taken not to introduce bias when detecting AEs and/or SAEs. Open-ended and non-leading verbal questioning of the subject is the preferred method to inquire about AE occurrences.

An abnormality identified during a medical test (e.g., laboratory parameter, vital sign, ECG data, physical exam) should be identified as an AE only if the abnormality meets 1 of the following criteria:

- Induces clinical sign or symptoms
- Requires active intervention
- Requires interruption or discontinuation of study medication
- The abnormality or investigational value is clinically significant in the opinion of the investigator.

MAAEs are AEs for which the subject has received medical attention by medical personnel, or in an emergency room, or which led to hospitalization. For each reported AE, the investigator will ask the subject if such medical attention has been received. In addition, the investigator will assess each MAAE if it constitutes a new-onset chronic disease (NOCD), defined as a MAAE which a) was absent at baseline, b) is not resolved at the follow-up telephone call, c) requires continuous medical care or attention. The investigator will also assess if any MAAE constitutes a PIMMC. PIMMCs are defined as any AEs of autoimmune

02 Dec 2019 Astellas Page 59 of 111

or auto inflammatory nature. The investigator will record MAAEs, NOCDs and PIMMCs in the AE eCRF.

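### The data listed for within-stage dose escalation stop at Day 7, but the severe-AE criterion they serve has no day limit and AEs are collected to Day 30

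*Protocol*

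**What the plan says.** Protocol 5.1.2 and the synopsis give the DEC two data sources for moving to the next dose within a stage: Day 7 data from the current cohort, and "Day 7 reactogenicity and safety data from all subjects of the preceding cohort(s"). Protocol 2.2.1 and SAP 7.6 also tie these decisions to Day 7.

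Under the escalation criteria in 5.1.2, the dose may not go up if, among ASP3772 recipients, "Two or more subjects experience an AE of severe intensity related to ASP3772". No day limit is attached. Under 5.5.1, "AE collection begins after the signing of the ICF and will be collected until 30 days after study vaccine administration".

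For the move from Stage 1 to Stage 2, the same section adds "Day 30 safety data (AEs, ECG, clinical laboratory tests and vital signs) from all subjects in Stage 1".

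In 5.1.5 the only stopping rule written for severe AEs is "One of the sentinel subjects experiences an AE of severe intensity related to ASP3772, when sentinel subjects are required". Attachment 1 (item 6, rationale) records that sentinels are no longer required from Cohort 5 onward.

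**The concern.** The listed data are narrower than the criterion they are meant to inform. A related, severe, non-serious AE that starts on Day 8 or later counts toward the criterion but is not in the listed package. This applies to preceding cohorts, all of whose subjects are past Day 7 when a later cohort is reviewed. It applies equally to early enrollees of the current cohort, who received the higher and adjacent dose and may also be past Day 7 at the decision. The Stage 1-to-2 list shows that later data were named where they were wanted.

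The step most exposed is Cohort 5 to Cohort 6, which opens 5 µg in subjects aged 65 to 85. The DEC could take that decision from the listed package without having been given late severe events that bear on it.

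**Working it through.** **1. What is covered without Day 8-30 AE data**

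| Event in an ASP3772 subject | Covered by |
|---|---|
| Related SAE, any day | 24-hour reporting (5.5.5); one case pauses dosing (5.1.5) and blocks escalation (5.1.2) |
| Related Grade 3+ laboratory abnormality in two or more subjects | Stopping rule, no day limit (5.1.5) |
| Solicited reaction, Days 1-7 | Day 7 package (5.1.2) and stopping rule (5.1.5) |
| Related, severe, non-serious AE to Day 7 | Day 7 package (5.1.2) |
| Related, severe, non-serious AE after Day 7 | Counts under 5.1.2, but not in the listed data; the stopping rule covers sentinels only |

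Only the last row is open. 'Severe' here means inability to perform daily activities (5.5.4). A solicited reaction that lasts beyond 7 days is recorded as an AE (5.4.3), so persistent reactions can also fall in this row.

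**2. Other routes to the DEC**

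- 4.4.1: for AEs that could prohibit escalation, severe AEs included, "the study vaccine assignment for these subjects will be revealed to determine if these events are related to ASP3772". This presupposes that such AEs are brought forward but does not say how.
- 4.4.1 also sets a 10% trigger for checking an imbalance of unsolicited AEs. In a 132-subject cohort that is 0.10 × 132 = 13.2, so 14 subjects, far above the two that block escalation.
- 7.9: safety data go to the DEC after each cohort, with no Day 7 cap and no stated content.
- Membership: 2.2.1 says sponsor medical, pharmacovigilance and statistics staff will sit on the DEC; the synopsis and 10.1 say may. Visit data are due in the eCRF within 5 days (8.1). Under 10.1 the investigator shares in escalation decisions.
- Discretion: the DEC decides "Depending on the nature, frequency and severity of the safety profile observed in the study" (5.1.2).
- Charter: "Further details around the dose escalation process are located in the DEC charter". It is not among the documents.

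None of these is a stated requirement to supply AEs after Day 7.

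**3. Size (illustration only)**

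The plan gives no operating characteristic for the rule, so there is no figure to reproduce.

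Inputs: 99 ASP3772 subjects per Stage 2 cohort and 30 per Stage 1 cohort (2.2.1); threshold of two subjects (5.1.2), which is 2/99 = 2.0%. Assumptions: a Day 8-30 risk p of 0.5%, 1% or 2% per ASP3772 subject; uniform hazard over those 23 days; counting within one cohort, since the documents do not say whether the count is per cohort or cumulative.

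Formula: P(X ≥ 2) = 1 − (1 − p)^n − n·p·(1 − p)^(n−1).

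Example, n = 99 and p = 0.01: 1 − 0.3697 − 0.3697 = 0.261.

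Minimum follow-up for Cohort 4 at the 5-to-6 decision: if Cohort 5 were dosed on the day the last Cohort 4 subject reached Day 7, with no enrolment or review time, that subject would be at Day 7 + 6 = Day 13. Days 8-13 are 6 of 23 days, so p becomes p × 6/23 = 0.00130, 0.00261 or 0.00522.

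| Assumed Day 8-30 risk | n = 99, Days 8-13 only | n = 99, full Days 8-30 | n = 30, full Days 8-30 |
|---|---|---|---|
| 0.5% | 0.8% | 8.8% | 1.0% |
| 1% | 2.8% | 26.1% | 3.6% |
| 2% | 9.5% | 59.1% | 12.1% |

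Real follow-up of Cohort 4 would exceed Day 13, because Cohort 5 takes time to enrol. Against that, Table 2 schedules no visit between Day 7 and Day 30, so only events reported by the cut could be added.

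**The case against.** The strongest reply is that the criterion itself closes the gap. It has no day limit, so two known late events already prohibit escalation, and a DEC that escalated regardless would breach 5.1.2. This stands. A reader might infer that the protocol permits escalation to 5 µg when late events are known to meet the criterion; the documents do not support that. What is left concerns supply: whether the events are put in front of the DEC.

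On supply, it can be said that sponsor safety staff sit on the DEC, that 4.4.1 expects severe AEs to surface, that 7.9 has no Day 7 cap, and that a charter may well call for cumulative listings. All of this is possible. A reader might also infer that late events will in fact be missed; without the charter that cannot be shown. The documents show only that the protocol and SAP do not require the review.

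A third reply is that the Day 7 gate is deliberate and repeated throughout the design. That is a sound reason to keep Day 7 as the trigger. It does not explain leaving out later data that already exist at the cut.

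Finally, the probabilities rest wholly on assumed rates, and a vaccine with such rates might also produce earlier severe events that block escalation. That is fair, and the grade does not rest on them.

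**Conclusion.** The mismatch is real but minor. Section 5.1.2 and the synopsis list a data package narrower than the criterion it serves, and no text in the protocol or SAP requires related, severe, non-serious AEs after Day 7 to reach the DEC. The residual risk is small. More serious events and early reactions are covered elsewhere, and before any elderly dosing the DEC has reviewed adults at 1, 2 and 5 µg to Day 30. That reassurance is partial, because Stage 2 admits 65- to 85-year-olds with stable chronic disease.

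The range of 0.8% to 59% shows only how strongly the answer depends on rates and follow-up that the documents do not give. It should not be read as an estimate of the chance of a wrong escalation. The conclusion rests on the wording of the documents, and it would shrink to an alignment of wording if the charter already requires cumulative data.

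**What to change.** Keep the Day 7 completion trigger, the minimum numbers (38 and 129 subjects), the criteria and the doses. Change both data bullets in 5.1.2 and the synopsis so that the DEC reviews Day 7 data plus all other safety data available at the data cut, from the current cohort and all preceding cohorts, including AEs after Day 7. Mirror this in SAP 7.6. Changing only the preceding-cohort bullet would leave out early enrollees of the current cohort.

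Cost: one cumulative listing per review; slightly wider use of the expedited eCRF entry in 8.1 (preferably 24 hours, against 5 days otherwise); and possibly a few more individual assignments revealed to the DEC under 4.4.1. There is no added waiting time, because only data available at the cut are used.
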